**[name]**

**Principal Investigator: [name]**

## 1. OBJECTIVES

Our objectives are to determine if exposure to the VA's firearm safety messaging is associated with changes related to cognitive and behavioral outcomes reported below (e.g., injury; firearm safety practices). Comparisons of findings may be made across those exposed to the VA firearm safety message and those exposed to a health promotion (comparison) video.

## 2. RESEARCH DESIGN & METHODS

### **DATA**

Data were collected by GfK Group, a U.S. market research firm, on behalf of the VA to pilot test the Firearm Safety messaging with a sample of Veterans. While the majority of participants were exposed to the firearm safety message, subsamples were also exposed to a health promotion video to serve as a comparison. The survey was carried out by GfK using sample from their KnowledgePanel®, a probability-based web panel designed to be representative of the United States. KnowledgePanel® is the largest online panel that relies on probability-based sampling techniques for recruitment; hence, the largest national sampling frame from which fully representative samples can be generated to produce statistically valid inferences for study populations. GfK panel provides samples with the highest level of representativeness available in online research for measurement of public opinions, attitudes, and behaviors. The panel was first developed in 1999 by Knowledge Networks, a GfK company. Panel members are randomly selected so that survey results can properly represent the U.S. population with a measurable level of accuracy, features that are not obtainable from non-probability panels.

The survey was administered online at two time points (pre/post message exposures) with a nationally representative sample of U.S. adult Veterans (18+, non-institutionalized) that belong to the GfK KnowledgePanel®. Military service status was determined using GfK's profile data. All data are de-identified and no personal or health information is included in the dataset. The GfK survey was designed to provide preliminary insights to the VA on message response. Demographic characteristics were also provided in the dataset. A de-identified analytic dataset has been received by the PI from GfK, and is currently stored in an access restricted file on the secure drive behind the VA firewall.

### **RESEARCH DESIGN:**

**Sampling:** GfK Group uses scientific random probability-based sampling techniques for recruitment of U.S. households. This probability-based sampling methodology improves population coverage, and provides a more effective sampling infrastructure for recruitment of hard-to-reach individuals, such as young adults and those from various minority groups. It should be noted that under this recruitment, households without Internet connection are provided with a web-enabled device and free Internet service. Once panel members are recruited and profiled by taking the Core Profile Survey, they become eligible for selection for surveys. Generally, the specific survey samples represent an equal probability selection method (EPSEM) sample from the panel for general population surveys.

**Data Collection:** To sample the population, GfK sampled eligible adults limited to one member per household. Selected panel members received an email invitation to complete the Baseline survey and were asked to do so at their earliest convenience. In the Baseline survey, each panel member was randomly assigned to one of three survey conditions. Next, panel members were then asked to view a

message based on the survey condition assigned. Finally, panel members were asked to complete the same survey 3-weeks post-baseline to determine how the video exposure may have influenced their opinions at exit.

Data included in the analytic file were collected from 12/15/2015 through 1/5/2016. The dataset includes responses from 474 participants that completed the baseline survey, with 358 of these participants also successfully completing the subsequent message exposures and exit survey within 3 weeks post-baseline.

**Waivers of Consent & HIPAA Authorization:** A consent waiver has been submitted for consideration. We believe this waiver does not adversely affect the rights or welfare of the participants as survey topics are minimally invasive and do not request identifiable information. Individuals also have several opportunities to opt out of participation during the recruitment process. A waiver of HIPAA Authorization has also been submitted to the IRB as no PHI or PII is collected as part of the survey. Analytic data files will be limited with no PHI or PII included.

Despite the request for waivers, each participant will still receive study information including a detailed description of purpose, procedures, risk/benefits, and voluntary nature. Prior to moving forward with any study procedures, participants will confirm their understanding of the study and their willingness to participate.

#### **ANALYSIS PLAN:**

All data analyses will be conducted at the VISN2 Center of Excellence for Suicide Prevention (COE) at the Canandaigua VAMC. All analyses will use data from the de-identified GfK dataset. The project under approval of this protocol will make no attempt to link data from GfK with any additional resources containing identifiable information. All analysis will be restricted to participants who are 18 years or older. Statistical analysis methods will include frequencies and standard deviations to describe sample characteristics. Bivariate analysis will be utilized to identify potential covariates to include in the multivariate models. Multivariate modeling will be used to examine hypotheses concerning the different effects of exposure on changes in outcomes across and within study conditions/groups. Changes in outcomes for each aim will be modeled over time for each condition, controlling for covariates of interest. Appropriate contrasts will then be used to identify significant differences in outcomes (as appropriate). All data management and analyses will be conducted by experienced team members listed on this protocol using SAS 9.4 (Cary, NC). Further ad hoc analyses may be conducted as needed.

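### Covariates for the randomized comparison are to be chosen by bivariate screening of the same data, with no limit to pre-exposure variables; the harm runs from negligible to material, depending on choices the plan leaves open

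*Combined protocol and SAP*

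**What the plan says.** Under Research Design (Data Collection), the protocol states: "In the Baseline survey, each panel member was randomly assigned to one of three survey conditions". The Analysis Plan then gives one sentence on how adjustment variables are found: "Bivariate analysis will be utilized to identify potential covariates to include in the multivariate models". Their use follows: "Changes in outcomes for each aim will be modeled over time for each condition, controlling for covariates of interest". Screen and model share one source: "All analyses will use data from the de-identified GfK dataset".

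The plan does not say whether the bivariate analysis is against outcome, condition or both. It gives no cutoff or candidate list and no requirement that a covariate precede the message. The Data section says that "Demographic characteristics were also provided in the dataset" but does not itemize them, and it records that the investigator already has the file. The exit survey repeats the baseline survey, so post-exposure answers to the same items are in that file.

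**The concern.** Random assignment makes baseline differences between conditions, as assigned, a matter of chance. A screen for such differences therefore picks covariates largely at random with respect to prognosis and drops most of those that would sharpen the estimate. A screen against the outcome keeps prognostic variables, but uses the data that are then tested and can give a different set for each outcome. If target and cutoff are open, several defensible models exist for each outcome, and the error rate depends on how one is picked.

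The missing limit to pre-exposure variables is a separate matter, because it concerns bias. The Objectives cover cognitive and behavioral outcomes. An exit attitude is likely to be associated with an exit behavior and so to pass a bivariate screen. If the message changes that attitude, adjusting for it removes part of the effect the study sets out to measure.

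**Working it through.** **Inputs from the documents.** 474 completed baseline and 358 also completed the exit survey: 358/474 = 75.5%, so 116 (24.5%) were lost. There were three conditions, most participants seeing the firearm message. No alpha, effect size, allocation ratio or covariate list is stated, so there is no figure of the plan's to reproduce.

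**Assumptions.** Completers split 239:119; outcome SD 1; two-sided 0.05; 12 independent baseline candidates, each correlated ρ with the outcome, so joint R² = 12ρ²; screening at p<0.10; effect 0.30 SD.

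**1. Fixed set, by formula.** Unadjusted SE = √(1/239 + 1/119) = 0.112, and power = Φ(0.30/0.112 − 1.96) = 76%. With p = 12 covariates fixed in advance, SE ≈ √[(1 − R²)(1/239 + 1/119)(n − 3)/(n − 3 − p)], where (n − 3)/(n − 3 − p) = 355/343:
- R² = 0: SE 0.114, power 75%.
- R² = 0.12: SE 0.107, power 80%.
- R² = 0.48: SE 0.082, power 95%.

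**2. Screen on imbalance between conditions.** By chance it admits about 12 × 0.10 = 1.2 covariates, whatever their prognostic value, so power stays near the unadjusted 76%. Simulation (4,000 replicates):

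| ρ | Joint R² | Power, condition screen | Power, fixed set |
|---|---|---|---|
| 0 | 0 | 76% | 75% |
| 0.05 | 0.03 | 76% | 76% |
| 0.1 | 0.12 | 76% | 79% |
| 0.2 | 0.48 | 80% | 95% |

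The screened test is also somewhat conservative: type I error is 3.1% at ρ = 0.2 and 4.2% at ρ = 0.1.

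A second set-up keeps the baseline outcome in every model (correlation 0.6 with the exit outcome), with ten further candidates, four of them prognostic (joint R² 0.10), and a screen at p<0.05. The SE is 0.090 screened against 0.083 with the prognostic covariates fixed (0.090/0.083 = 1.08). Power at 0.25 SD is 80% against 86%. The loss is 6 points because those covariates explain 0.10/(1 − 0.36) = 16% of what the baseline leaves unexplained.

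**3. One locked outcome screen on baseline variables.** Type I error was 4.4-5.8% across all runs. The Monte Carlo standard error is about √(0.05 × 0.95/4,000) = 0.3 points.

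**4. Free choice, smallest p-value kept.**
- Best of four (unadjusted; outcome screen at 0.05, 0.10 and 0.20): 5.8%, 7.6% and 8.7% at ρ = 0, 0.1 and 0.2. A repeat run gave 6.6-8.5%.
- Best of ten screens with the baseline outcome always in: 7.5-8.7% for firearm shares of 0.50 to 0.80.
- Best of five sets where even the baseline outcome may be left out: 9.2-10.3%.

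**5. An exit item on the causal path.** Total effect = direct effect + (message effect on the item) × (item effect on the outcome). Adjusting for the item leaves only the direct part:
- 0.15 + 0.40 × 0.5 = 0.35; adjusted 0.15; power 87% to 33%.
- 0.10 + 0.40 × 0.4 = 0.26; adjusted 0.10; power 81% to 25%.
- 0.20 + 0.40 × 0.3 = 0.32; adjusted 0.20; power 96% to 71%.

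The size of each drop follows from the coefficients assumed. Only the direction is general, for an item that carries part of the effect.

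**The case against.** The sentence speaks of potential covariates. It names no significance test, and the next step refers to covariates of interest, which leaves room for subject-matter judgment. The survey was meant to give preliminary insights. Covariate work is not pointless here either: a quarter of the baseline sample is missing at exit, and the within-condition analyses are not randomized comparisons.

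Much of this stands, and it rules out four stronger readings that a reader might infer.
- *The plan forfeits about 15 points of power.* That needs a screen on condition and a joint R² of 0.48. Nothing in the documents supports such prognostic strength for panel demographics, and modeling change over time may already bring in the baseline outcome.
- *The plan inflates type I error.* A single locked outcome screen does not do so to any important degree. The 6-9% arises only if the most favorable model is kept, which the plan neither states nor intends.
- *Exit items will be used as covariates.* No section proposes this; the plan only fails to exclude it.
- *Randomization leaves nothing to adjust for.* It protects the groups as assigned, not necessarily the 358 completers.

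What does not stand is that the text is harmless as written. No second step or rule follows the screen, contrasts are left open, further ad hoc analyses are allowed, and the plan still looks for significant differences. Possible imbalance from dropout calls for named baseline predictors; a significance screen can miss these.

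**Conclusion.** The concern holds as a weakness of method whose cost is conditional. The plan does state a selection route, bivariate analysis in the same data, for a randomized comparison, and no other section limits it. A fixed pre-exposure set is better and costs almost nothing.

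On the assumed inputs, a condition screen loses 0 to 3 points of power at joint R² up to 0.12, 6 in the set-up with the baseline outcome included, and about 15 at joint R² 0.48. A locked outcome screen on baseline variables does little harm. Unrestricted choice takes type I error to about 6-9%, or about 10% if the baseline outcome is itself optional. Bias from an exit item is the most serious possibility but also the least certain to occur. The textual gap is certain. The magnitudes rest on an assumed allocation, effect size, alpha and covariate strength, none of which the documents give. This should be corrected, but it is not grounds for setting the study aside.

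**What to change.** Replace the screening sentence with a rule to this effect:
- Every between-condition model uses the same covariate set: the baseline value of the outcome (where the over-time model does not already use it) plus pre-exposure demographics, listed by name from those actually in the GfK file and including likely predictors of dropout.
- No covariate is added or dropped on a significance test.
- No variable measured after message exposure enters the model for the effect of condition.
- Bivariate tables are descriptive only, and the unadjusted contrast is reported beside the adjusted one.

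Because the data are already held, the list should be fixed and dated before outcomes are examined by condition. If that is no longer possible, label the analysis exploratory.

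The cost is a few sentences, no new data and a few degrees of freedom. If all 12 assumed covariates were useless, the SE would rise from about 0.112 to 0.114.

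### The analysis plan does not commit the randomized between-condition comparison to adjustment for the baseline answer to the same item, which can leave avoidable variance

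*Combined protocol and SAP*

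**What the plan says.** Under RESEARCH DESIGN (Data Collection), "each panel member was randomly assigned to one of three survey conditions", and "panel members were asked to complete the same survey 3-weeks post-baseline". The same section reports "474 participants that completed the baseline survey, with 358 of these participants also successfully completing" the exit survey. The DATA section adds that "the majority of participants were exposed to the firearm safety message", with subsamples shown a health promotion video. No arm sizes are given.

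Section 1 (OBJECTIVES) names the between-condition question in permissive terms: "Comparisons of findings may be made across those exposed to the VA firearm safety message and those exposed to a health promotion (comparison) video". The ANALYSIS PLAN then uses multivariate models to "examine hypotheses concerning the different effects of exposure on changes in outcomes across and within study conditions/groups".

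On the form of those models there are two sentences: "Bivariate analysis will be utilized to identify potential covariates to include in the multivariate models", and "Changes in outcomes for each aim will be modeled over time for each condition, controlling for covariates of interest". Contrasts follow but are not specified. The baseline answer to the item is not named as a covariate, and neither analysis of covariance nor a common baseline mean is mentioned. The target of the bivariate screen (exit answer, change or condition) is not stated.

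**The concern.** In a randomized comparison with the same item measured before and after, the baseline answer is usually the strongest available predictor of the exit answer. A change score uses it with a fixed coefficient of 1. Regression on the baseline answer uses the coefficient that minimizes the variance of the contrast. The two coincide only if the baseline-exit correlation is 1 (with equal variances). A condition-by-time model that gives each condition its own baseline mean has much the same weakness, because it ignores that randomization makes those means equal in expectation.

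Data collection has closed, so precision for the firearm-message versus health-promotion comparison now depends on the model. The demographic covariates need not make good the loss: a characteristic that predicts the level of an answer equally at both times cancels out of a change score.

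**Working it through.** The documents state no power, effect size, SD, correlation or arm size, so there is no figure of theirs to reproduce.

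**Inputs from the documents.** 474 baseline records and 358 completers; retained fraction f = 358/474 = 0.755; 474 − 358 = 116 without exit data.

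**Assumptions.** Continuous item with SD 1 at both times; baseline-exit correlation r from 0.3 to 0.9; equal dropout by condition. For detectable differences: two-sided 5% level, 80% power, and three equal conditions (358/3 ≈ 119 each), compared as 239 vs 119 if two firearm-message conditions are pooled, or as 119 vs 119.

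**Variance factors for the contrast, per completer.**
- Change score: 2(1 − r).
- Baseline-adjusted: 1 − r².
- Free-baseline repeated measures: each condition's estimated change is (exit mean − r × baseline mean) in completers, minus (1 − r) × the baseline mean of all its records. The factor is therefore (1 − r²) + (1 − r)²f.

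Avoidable share against a change score: 1 − (1 − r²)/[2(1 − r)] = (1 − r)/2. Against the free-baseline model: (1 − r)²f / [(1 − r²) + (1 − r)²f].

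Worked at r = 0.5: the factors are 1.00 (change), 0.75 (adjusted) and 0.75 + 0.25 × 0.755 = 0.939 (free baseline). The avoidable shares are 0.25/1.00 = 25% and 0.189/0.939 = 20%.

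| r | Avoidable, vs change | Avoidable, vs free baseline | Change on 358 equals adjusted on | Detectable SD, 239 vs 119: change / free / adjusted | Detectable SD, 119 vs 119: change / adjusted |
|---|---|---|---|---|---|
| 0.3 | 35% | 29% | 233 | 0.373 / 0.357 / 0.301 | 0.432 / 0.348 |
| 0.5 | 25% | 20% | 269 | 0.315 / 0.305 / 0.273 | 0.365 / 0.316 |
| 0.7 | 15% | 12% | 304 | 0.244 / 0.240 / 0.225 | 0.282 / 0.260 |
| 0.8 | 10% | 8% | 322 | 0.199 / 0.197 / 0.189 | 0.231 / 0.219 |
| 0.9 | 5% | 4% | 340 | 0.141 / 0.140 / 0.137 | 0.163 / 0.159 |

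The fourth column is 358 × (1 − avoidable share). A simulation of 239 vs 119 (4000 runs) gave adjusted-to-change variance ratios of 0.628, 0.744 and 0.862 at r = 0.3, 0.5 and 0.7, against 0.65, 0.75 and 0.85 from the formula.

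**Demographic covariates.** If demographics explain a share q of the level equally at both times and are in both models, the residual correlation is r′ = (r − q)/(1 − q) and the avoidable share is (1 − r′)/2. At q = 0.1 this is 39/28/17/11/6% across the five values of r, so adding them does not close the gap.

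**Would the screen bring the baseline answer in?** Simulated with an assumed p < 0.05 rule (239 vs 119, 10,000 runs per r), the baseline answer was kept in 100% of runs when screened against exit, in 98–100% when screened against change, and in about 5% when screened against condition (about 20% at p < 0.20).

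**Type I error.** Simulated null rejection was 4.9–5.2% for the change score, 4.7–5.3% for the adjusted model and 4.1–4.9% for the condition-screened model. Only these three were simulated.

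**Binary items.** With an assumed 50% answering yes at baseline and a log-odds effect of 0.8, simulated power with and without baseline adjustment was 92% vs 74%, 86% vs 73% and 68% vs 61% at baseline-exit correlation 0.3, 0.5 and 0.7. The direction is the useful part; the values depend on the settings.

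**The case against.** The strongest reply is that the plan does not rule out the better model. Controlling for covariates of interest could include the baseline answer, in which case a change-score regression gives the same linear condition contrast as regressing the exit answer on it. A screen against exit or change would nearly always select it. This stands: a reader might infer that the plan will omit baseline adjustment, and the documents do not show that. What remains is that precision turns on an unstated choice.

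Second, the between-condition comparison is only something that may be made, in a pilot dataset, and for stable answers the gain is small (0.199 to 0.189 SD at r = 0.8 with 239 vs 119). This stands too and limits the importance of the point. The larger gains need r of 0.3 to 0.5, and the documents give no r.

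Third, the outcomes may be binary or ordinal. The percentages then do not apply, and a baseline-adjusted odds ratio is a different quantity from a marginal one. In one simulated case (119 vs 119, correlation 0.7, same 50% and 0.8 assumptions) the adjusted odds ratio was 2.23 and the marginal 1.53, with estimate-to-SD ratios of 2.10 and 2.05. The caution about scale stands. The inference that adjustment is of no use for such items does not: the gain was small in that case but clear at lower correlations.

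A reader might also infer confounding, or an inflated error rate caused by the bivariate screen. Conditions were randomized, so an unadjusted change contrast is not confounded. The loss described here comes from the model form, not from the screen.

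**Conclusion.** The point holds as one of precision and pre-specification. The plan has a randomized comparison and a repeated item but does not commit to using the baseline answer efficiently. On the literal reading with no baseline covariate, a continuous item loses between 5% and 35% of the contrast's variance to a change score, or 4% to 29% to a free-baseline model, for r from 0.9 down to 0.3. The loss is zero if the baseline answer is in the model or a common baseline mean is imposed. Every r and split is assumed, and the percentages are for continuous items only. The gap is modest, but worth closing because doing so costs almost nothing.

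**What to change.** In the ANALYSIS PLAN, directly after the sentence on modeling changes over time for each condition, add:

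> For each between-condition comparison, the main model will be the exit answer regressed on randomized condition and the baseline answer to the same item (linear, logistic or ordinal as the item requires). For continuous items a repeated-measures model with a common baseline mean may be used instead. The baseline answer is included regardless of the bivariate screen.

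Keep the within-condition change analyses and their covariate selection as planned. The cost is the added wording and a little SAS code, with no new data. For logistic or ordinal items the adjusted odds ratio is conditional on the baseline answer and should be reported as such.

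### The analysis plan tests outcomes for significance across and within three conditions, with no primary outcome, primary contrast, multiplicity rule or exploratory label, although the exit data were already held

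*Combined protocol and SAP*

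**What the plan says.** Section 1 (Objectives) sets out to relate exposure to the firearm safety message to "cognitive and behavioral outcomes reported below (e.g., injury; firearm safety practices"). No later section contains the promised list; the two examples in the parenthesis are all there is. Section 1 also makes the comparison with the health-promotion video optional.

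Under Research Design, "each panel member was randomly assigned to one of three survey conditions". The three conditions are not defined individually.

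The Analysis Plan then gives the testing strategy:

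- Scope: models will examine "different effects of exposure on changes in outcomes across and within study conditions/groups".
- Outcomes: "Changes in outcomes for each aim will be modeled over time for each condition, controlling for covariates of interest". No aims are listed.
- Covariates: "Bivariate analysis will be utilized to identify potential covariates to include in the multivariate models".
- Criterion: "Appropriate contrasts will then be used to identify significant differences in outcomes (as appropriate").
- Additions: "Further ad hoc analyses may be conducted as needed".

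On timing, the Data section says "A de-identified analytic dataset has been received by the PI from GfK". Research Design gives the collection period as 12/15/2015 to 1/5/2016, with 474 baseline respondents, of whom 358 also completed the exit survey.

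**The concern.** The plan makes statistical significance the criterion for a difference but does not say which outcome and which contrast carry the main conclusion. In a plan written before data collection, that gap could be closed neutrally later. Here the exit responses were in hand, so whoever closes it may already know, or can find out, which choice gives a favourable result. Item, coding, direction, covariates and contrast can all be chosen at that stage in full compliance with the plan.

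Two consequences follow. A significant change on one outcome could not be told apart from selection among several. And a favourable attitude result could take the place of a null result on firearm safety practices, with nothing in the plan to show the switch. Because the between-group comparison is optional, a within-condition pre/post change could also be presented as associated with exposure, although such a change does not use the randomised comparison.

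**Working it through.** **Is there a figure to reproduce?** No. The documents give no significance level, power, effect size or target sample size; 474 and 358 are achieved counts.

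**Inputs**

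- From Research Design: three conditions, hence 3 × 2 / 2 = 3 pairwise contrasts per outcome. The allocation ratio is not stated.
- Not in the documents, so assumed: two-sided 5% per test, no true effect, and k = 5, 10 or 20 outcomes with correlation 0, 0.5 or 0.8.

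**Step 1. One contrast, k independent outcomes.** P(at least one false positive) = 1 − 0.95^k.

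- k = 5: 1 − 0.95^5 = 0.226
- k = 10: 1 − 0.95^10 = 0.401
- k = 20: 1 − 0.95^20 = 0.642

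**Step 2. One contrast, correlated outcomes.** Items from one survey on related topics will rarely be independent. Equally correlated normal test statistics were simulated (200,000 replicates), counting replicates in which any absolute value exceeded the two-sided 5% limit.

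| Outcomes | Correlation 0 (formula) | Correlation 0.5 | Correlation 0.8 |
|---|---|---|---|
| 5 | 22.6% | 18.2% | 12.9% |
| 10 | 40.1% | 28.9% | 17.3% |
| 20 | 64.2% | 42.0% | 22.4% |

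**Step 3. One outcome, all three pairwise contrasts.** Simulation (400,000 replicates) gives 12.3% with near-equal groups (119, 119, 120). With an assumed unequal split of the 358 completers (150, 150, 58) it gives 12.1%, so the unknown allocation matters little here.

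**Step 4. Both sources together, outcomes independent.** 1 − (1 − 0.1226)^5 = 0.48 for 5 outcomes and 1 − (1 − 0.1226)^10 = 0.73 for 10. Correlation between outcomes would lower these.

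**Not counted:** within-condition tests, covariate selection and ad hoc analyses, any of which could raise the figures.

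**Step 5. After the change.** One named outcome on one named contrast has a 5% false-positive chance. For the secondary list, the first Holm step is 0.05/m: 0.01 for m = 5 and 0.005 for m = 10.

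**The case against.** The strongest reply is that this is pilot work. The Data section describes a survey meant to give early insight into message response, and the Objectives speak of association. Strict multiplicity control is often left out of such work, and defensibly so. That softens the consequence but does not remove it: the Analysis Plan refers to effects of exposure and to significant differences, and nowhere labels its tests exploratory.

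Three stronger readings are tempting and should be resisted.

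- A reader might infer that results by condition were examined before the plan was written. The documents show receipt and restricted storage, not inspection.
- A reader might infer that the plan makes every survey item eligible, or tells the analyst to screen them all. It does not: outcomes are limited to cognitive and behavioural ones tied to aims, and contrasts follow a model over time. The set is undefined rather than declared unlimited. The approach can yield false-positive claims; it need not.
- A reader might take 64% as this study's error rate. It is one corner of an assumed grid; 20 outcomes at correlation 0.8 give 22%.

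It may also be said that aims or outcomes were lost from a longer text: section numbers jump from 2 to 4, and the references have no visible in-text citations. That does not clearly explain the gap, since the outcomes are promised after the Objectives and no later section supplies them.

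Finally, no questionnaire is shown, and Research Design says the exit survey concerns opinions. A usable practice item therefore cannot be taken for granted. This stands, and it shapes the fix.

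**Conclusion.** The concern holds as a fault in what the plan permits. Significance testing without a primary outcome, primary contrast, multiplicity rule or exploratory label leaves the main claim open to choice after results are known, and prior possession of the exit data makes that more than missing detail. Whether any such choice was made is not shown.

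The size is a range, because neither the number of outcomes nor the significance level is given. For 10 to 20 outcomes on one contrast it runs from about 17% (10 outcomes, correlation 0.8) to about 64% (20 outcomes, independent), against a nominal 5%. These figures rest on assumed two-sided 5% tests, no true effect and equal correlation between outcomes.

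**What to change.** Amend the Analysis Plan before any exit outcome is tabulated by condition:

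1. Define the three conditions.
2. Name one primary outcome, with its item, coding and favourable direction. Firearm safety practices, the behavioural example in the Objectives, is the natural candidate if the survey has a usable item; otherwise name one cognitive outcome.
3. Name one primary contrast between randomised firearm-message and health-promotion assignment, stating which condition or conditions form each side, and test it at two-sided 5%.
4. List a short set of secondary outcomes and apply Holm within it. This holds the primary claim and the secondary list at 5% each, so at most 5% + 5% = 10% over both.
5. Report all other outcomes, within-condition changes and ad hoc analyses as exploratory, without significance claims.
6. State what had been seen of the data when these choices were made. If results by condition were already known, say so and report every outcome as hypothesis-generating, which fits the pilot purpose in the Data section.

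The cost is protocol wording, with no new data. Secondary outcomes face a stricter threshold. The single primary test may have limited power: 358 completers over three conditions is about 119 each if equal (358/3), and the Data section says most participants saw the firearm message, so the comparison side may be smaller.
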